Given the potential for Maraviroc to augment rehabilitation training, we will carry out a trial of Maraviroc in patients with disabilities severe enough to have required inpatient stroke rehabilitation and, based on our preclinical data, who can start the drug intervention within 6 weeks of stroke onset. We plan a parallel group, randomized controlled pilot trial at three sites, UCLA SOM, Yale University SOM in New Haven, and Burke Neurological Research Institute in White Plains, NY, to gather enough entries in a shorter time and to better generalize the results of this phase II/III pilot trial. We will compare usual post-stroke care plus placebo versus Maraviroc given for 8 weeks in 60 participants (up to 66 to account for dropouts). The primary outcome measurements will be gains in walking and functional use of the affected upper extremity, continuously monitored remotely, as well as formally assessed at 4 and 8 weeks after initiating the drug and at 6 months (primary endpoint) post stroke onset. To try to maximize the amount of practice that is most relevant to the primary outcome measurements and determine whether or not Maraviroc can enhance the effects of training, as hypothesized, all participants will be monitored by mobile health devices we developed and will receive weekly encouragement, based on device data, to walk, reduce sedentary time, and reach and grasp in the home in between usual care therapies. The amount of use of these telerehabilitation devices will be a nested substudy of feasibility.

We will look for a behavioral marker of the potential effect of Maraviroc by testing each subject while on and off the assigned medication with several commonly used neuropsychological tests of motor and hippocampal learning.

The trial will be registered at ClinicalTrials.gov with ethical approval from the UCLA medical IRB.

Hypothesis 1: Subjects who take Maraviroc plus outpatient and home-based rehabilitation therapy managed remotely will improve significantly more in the primary outcomes of walking speed and upper extremity function by the Action Research Arm Test (ARAT) compared to the placebo drug group at the 6-month post stroke assessment.

Hypothesis 2: The feasibility of home-based telerehabilitation practice will be revealed by the finding that at least 75% of all participants will have achieved compliance for at least 150 minutes of walking and 100 minutes of reach and grasp practice weekly.

Methods

Consent Process:

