walking speed, 6-min walking distance, a video-recorded assessment of upper extremity kinematics that does not show the subject's face, and Action Research Arm Test (ARAT). We will record the average two blood pressures and heart rates on the day of entry and the most recent HbgA1c and lipid panel, liver function tests, creatinine/BUN, and MRI/CT imaging results from the inpatient rehabilitation medical record. If liver function tests or creatinine cannot be found, the tests will be obtained at the outpatient research site as a cost to the study. [name] will review each imaging study to localize the relevant stroke lesion by consensus. An email address and phone number for the patient and a close contact will be kept separate from the clinical database by the coordinator.

Interventions:

Maraviroc: Medications are often in flux during inpatient rehabilitation, so Maraviroc or placebo will be started within two weeks of discharge, which most often will occur from 4-6 weeks after stroke onset. A 1-month supply of capsules will be handed to participants after the Consent has been signed, baseline measurements obtained, and randomization assigned, usually on the same day. The second 1-mo supply will be provided during a scheduled interim measurement assessment at UCLA near the end of the 4th week on medication. Pill counts will be taken on the returned bottle. Participants will take either *Maraviroc or a placebo at a dose of 300 mg at 6-8AM*. The capsules will be supplied by the UCLA, Burke and Yale pharmacies to each respective site and used under an IND and IRB protocol as required by each institution.

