Based upon Pfizer's reports on premarketing and post marketing studies of Maraviroc and our review of the literature, no dose adjustment is necessary in patients with even mild-to-moderate renal impairment. The drug does not affect the QT interval. At high doses (600mg or more), it may induce orthostatic hypotension, so it is recommended that *users who also take an anti-hypertensive medication be asked about symptoms of orthostatic hypotension*. Of note, 8% of patients in active and placebo drug groups described orthostatic symptoms in a large trial. In HIV trials, 1.3% of subjects had cardiovascular events, more than in the placebo group, but the link to the drug was unclear and symptoms occurred only in those with known cardiac disease. Also, no greater incidence of infection, rash or other CNS symptoms was noted in these subjects. An occasional Stevens-Johnson syndrome and drug rash with eosinophilia and systemic symptoms did occur (seen only in post marketing surveillance, not in controlled trials), so *complaints of rash, fever, joint or muscle aches, blisters, facial edema, etc. will be part of our weekly phone call surveillance plan*. Participants will be told to stop their medication immediately should such symptoms occur and their physician notified. Of note, St John's wort should not be used with the medication since it decreases the concentration of Maraviroc

The drug is metabolized by the liver, so using it in persons with more than mild hepatic disease, especially in the presence of a CYP3A inhibitor, would have to be closely monitored; our participants will be free of hepatic, as well as renal impairment. The recommendation from the FDA is to obtain liver function tests prior to starting the drug and again should symptoms such as rash or hepatitis occur. This rather rare adverse reaction tends to occur at about one month after starting the medication (in less than 4% on the drug or placebo) , so *we will obtain a bilirubin and transaminases at the planned 1-month follow up.*

Adverse events related to the medication assignment, to rehabilitation practice or to other causes will be adjudicated by the Safety Committee with input from the PI.

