A data manager at UCLA will review all incoming data from the 3 sites for completeness and quality, as well as ensure proper use of the systems (e.g. make sure devices are charged regularly, automatic data uploads occur without problems, and practice data are processed correctly). The study staff at each site will assist the UCLA staff to help solve technical problems with the equipment and interact with subjects around difficulties in patient participation. At the weekly call by UCLA staff, participants will be queried from a script about any possible medical complications. Such potential adverse events will be immediately reported to [name] who will contact his participants or contact the local PI at Burke or Yale to interview their subjects and then report back to [name].

Outcome Measurements:

The primary outcomes will be a timed walking speed over 10 meters by the blinded physical therapist and the ARAT for UE function performed by the blinded therapist. These will be obtained at baseline, then after 4 weeks on assigned medication, within 5 days of the last medication dose (8 weeks) and again at 6 months post stroke onset.

Secondary outcomes obtained at the end of drug treatment and at 6 months after stroke onset by the blinded observer will include the Fugl-Meyer Motor Assessment score for both lower and upper extremities, clinic-based 3-min walking distance, and the Stroke Impact Scale score related to quality of life. We will also assess for satisfaction and self-efficacy for practice and exercise (see Table). Exploratory studies will examine dose of practice based on LEAP data (duration, number of repetitions of reach and grasp of objects) and for walking (total daily walking practice time, sedentary time, and walking bouts of more than 5 minutes), and self-ratings about self-efficacy for exercise.

Statistical Analyses:

A recent observational trial (Lohse and Lang, 2016) found that walking speed increases at 0.1m/s per month and the ARAT increases by 2.9 points monthly within the time frame as this trial.

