Secondary Analyses: Secondary outcomes listed in the Table will be evaluated using t-tests, Wilcoxon rank sum tests, or chi-square tests as appropriate. One planned secondary analysis will compare outcomes based on whether or not participants can extend their wrist and at least 3 fingers at least 5 degrees at time of randomization, to assess for possible differences in drug responses between those with higher compared to lower levels of initial motor control. Another will compare outcomes in those who achieve the practice goals of Hypothesis 2 to those who do not in relation to drug assignment. We will not likely have enough subjects to do more than look for interesting potential future hypotheses.

Safety Committee:

A Safety Committee will serve both research sites. It will include the study statistician, a physician and an allied health clinician with training in stroke rehabilitation. It will meet before the start of the trial, every 6 months, after the first 10 subjects have completed the 2-month drug intervention, and as needed (e.g., serious adverse reaction).

Confidentiality:

All data will be entered from the study sites at UCLA, Yale and Burke into the RedCap database that will be monitored at UCLA by the study statistician for completeness. All materials related to the trial for UCLA entries will be stored in a locked cabinet in a locked room by the coordinator.

References

Dobkin BH. A Rehabilitation-Internet-of-Things in the Home to Augment Motor Skills and Exercise Training. *Neurorehabil Neural Repair*. 2016 Nov 23. pii: 1545968316680490.

Table. Measurement tools and testing schedule

Category	Test	Schedule		During treatment: at end of 4 and 8 weeks	6 mo outcomes
		Entry	Weekly f/u for 2 mo		
Study Procedures					
Screening	X	X			
Inclusion/Exclusion	X	X			
Informed Consent	X	X			
AE Assessment	X		X		
Demographics	NIH standard	X			
Disability	FIM	X			X
Mobility	10-m walk speed	X		X	X
Upper extremity fx	ARAT	X		X	X
Overall Impairment	NIHSS	X			X
Motor Impairment	Fugl-Meyer motor score	X		End of tx	X

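### No adverse-event questioning is scheduled after the 2-month weekly calls, so about 12–14 weeks before the 6-month primary endpoint have no planned AE collection

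*Combined protocol and SAP*

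**What the plan says.** In the table of measurement tools and testing schedule, the row "AE Assessment" has one mark under a time point, in the column headed "Weekly f/u for 2 mo". Its cells for entry, for the 4- and 8-week visits and for 6 months are empty. The 6-month column is in use: FIM, 10-m walk, ARAT, NIHSS, Fugl-Meyer and several questionnaires are all marked there.

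The text of the Interventions section fits the table. Under Maraviroc, the symptoms suggestive of a serious drug reaction "will be part of our weekly phone call surveillance plan". The same part adds one safety laboratory check: "we will obtain a bilirubin and transaminases at the planned 1-month follow up". The closing paragraph of Interventions says: "At the weekly call by UCLA staff, participants will be queried from a script about any possible medical complications". The text gives these calls no end date, so the 2-month limit comes from the table header.

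On review of events, the Maraviroc part is broad: "Adverse events related to the medication assignment, to rehabilitation practice or to other causes will be adjudicated by the Safety Committee". It names no time window. The Safety Committee section sets meetings before the start, every 6 months, after the first 10 participants finish treatment, and as needed. It does not say how events after treatment are to be collected.

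**The concern.** Aims sets the primary endpoint at 6 months after stroke, well after the last dose. Both primary outcomes, 10-m walking speed and ARAT, are performance tests. A recurrent stroke, a fall with injury or a hospital stay between the end of treatment and that visit could change either one directly. With 30 evaluable participants per arm, a handful of such events falling unevenly could colour the comparison, and the analyst would want to know who had them, when and why.

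The plan also intends more than its schedule delivers. It wants events from the drug, from practice and from other causes adjudicated, but an event that nobody asks about may never reach the Safety Committee. The Maraviroc part itself reports more cardiovascular events on drug than on placebo in HIV trials, with an unclear link and only in people with known cardiac disease. In a stroke population that is a reason to ask about vascular events up to the endpoint.

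**Working it through.** The plan states no figure on this point, so there is none to reproduce. The check has three parts.

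**1. Is the blank 6-month cell real?** The AE row carries a second X in the Test column, where no time point belongs. The Screening, Inclusion/Exclusion and Informed Consent rows have the same stray X, so it looks like a feature of the table. If the AE row were nevertheless one column too far left, its two marks would fall at entry and at 4/8 weeks, and the 6-month cell would still be empty. A shift of two columns would be needed to reach 6 months. Applied to the Informed Consent row, that shift would put consent at the weekly calls and the 4/8-week visits, which makes no sense. The reading therefore stands.

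**2. How long is the stretch without planned AE questions?** Inputs:
- Drug start, week *s* after stroke: "which most often will occur from 4-6 weeks after stroke onset" (Interventions, Maraviroc).
- Treatment duration: 8 weeks (Aims).
- Primary endpoint: 6 months after stroke (Aims), taken here as 26 weeks.
- Weekly calls: 2 months (table header), taken as the 8 treatment weeks. If 2 months means a third of 26 weeks, it is 26/3 = 8.7 weeks, and each gap below is about 0.7 week shorter.

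Formulas: last dose at week *s* + 8; gap = 26 − (*s* + 8) = 18 − *s*; share of the time from drug start to endpoint = (18 − *s*)/(26 − *s*).

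| Start week | Last dose, week | Gap, weeks | Share |
|---|---|---|---|
| 4 | 12 | 14 | 14/22 = 64% |
| 5 | 13 | 13 | 13/21 = 62% |
| 6 | 14 | 12 | 12/20 = 60% |
| 8 (assumed) | 16 | 10 | 10/18 = 56% |

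The last row is a sensitivity case. Aims speaks of starting within 6 weeks, but the usual 4–6 weeks is not stated as a limit, and Consent Process allows contact with patients discharged less than 2 months after onset.

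**3. What kind of event falls in the gap?** Background gives a terminal half-life of 14–18 hours. Five half-lives are 5 × 14/24 = 2.9 days to 5 × 18/24 = 3.75 days, so drug exposure ends within days of the last dose. The gap is therefore mostly off-drug time. It chiefly concerns intercurrent events and delayed effects.

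The documents give no event rate for this period. For scale only, assumed per-person risks of 2%, 5%, 10% and 20% over the gap would mean 60 × risk = 1.2, 3, 6 and 12 participants of 60 with an event that no planned question would pick up.

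If AE questions were asked at the 6-month visit, planned coverage from drug start would rise from 8 of 20–22 weeks (36–40%) to the whole period.

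**The case against.** A reader might infer from the table that nothing at all is captured after the last dose and that later events cannot be identified by arm. The documents do not support that. Spontaneous reports are not excluded, and no text closes AE reporting at the end of treatment. The 6-month visit repeats NIHSS and FIM, where a disabling recurrent stroke would probably show, and these scores can be compared by arm. The note under the table asks for reasons for non-participation, which could explain some missed visits. The capsules are used under an IND and institutional IRB protocols, which may set reporting periods that cannot be checked here.

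A reader might also infer that events around the last dose are missed. That is weak too: weekly calls run through treatment, a visit takes place within 5 days of the last dose, and the half-life is short. It remains true that the AE cell for that visit is blank.

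Nor should 60–64% be read as a share of missed events. It is calendar time, mostly off drug, and rests on the usual start window.

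Finally, this is a pilot with no formal between-arm AE comparison specified, and asking actively about AEs only during treatment with a short-half-life approved drug is a defensible choice. That argues for a low rating but does not fill the gap. NIHSS and FIM give neither the date nor the cause of an event, and they would miss a fall or hospital stay that left no lasting deficit.

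**Conclusion.** The point holds as a cheap improvement. The schedule plans AE assessment only within the 2-month weekly follow-up, and no part of the plan schedules AE questions at the 6-month visit. For the usual start at weeks 4–6, with 26 weeks standing for 6 months, this leaves about 12–14 weeks before the primary endpoint without planned AE collection (about 10 weeks if a participant started at week 8). Some major events may come to light by other routes. What would be lost is a systematic record, by arm, of falls, hospital stays, and the timing and cause of recurrent events that bear on 6-month walking speed and ARAT. The number of such events is unknown. The power calculation and the primary analysis are unaffected.

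**What to change.** - In the schedule table, mark AE Assessment at the existing 6-month visit and at the existing end-of-treatment visit.
- At both, use the weekly-call script for events since the last call. Ask explicitly about recurrent stroke, falls and hospital stays, and record the start date and presumed cause.
- State the AE reporting period and the end of the weekly calls in the Interventions text, so that text and table agree.
- In Statistical Analyses, add a descriptive listing of AEs by arm, separately for the on-treatment and post-treatment periods.

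No new visit is needed and the sample size does not change. The cost is a few minutes at each of the two visits. The drawback is that recall over about 3 months is less complete than recall over a week, so the two periods should not be compared as if ascertainment were equal. The arms can still be compared within each period, because both are asked in the same way under blinding.
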